## Figures

Figure No.	Title	Population
IGA		
4.1.1	Proportion of Participants Achieving IGA-TS	ITT
4.1.1.1	Proportion of Participants Achieving IGA-TS by Baseline EASI Score	ITT
4.1.1.2	Proportion of Participants Achieving IGA-TS by Age	ITT
4.1.1.3	Proportion of Participants Achieving IGA-TS by Sex	ITT
4.1.1.4	Proportion of Participants Achieving IGA-TS by Race	ITT
4.1.1.5	Proportion of Participants Achieving IGA-TS by Region	ITT
4.1.1.6	Proportion of Participants Achieving IGA-TS by Prior Systemic Therapy	ITT
4.1.1.7	Proportion of Participants Achieving IGA-TS by Season Enrolled	ITT
4.1.2	Forest Plot of Response Rate Difference in Achieving IGA-TS at Week 8	ITT
EASI		
4.2.1	Proportion of Participants Achieving EASI75	ITT
4.2.1.1	Proportion of Participants Achieving EASI75 by Baseline EASI Score	ITT
4.2.1.2	Proportion of Participants Achieving EASI75 by Age	ITT
4.2.1.3	Proportion of Participants Achieving EASI75 by Sex	ITT
4.2.1.4	Proportion of Participants Achieving EASI75 by Race	ITT
4.2.1.5	Proportion of Participants Achieving EASI75 by Region	ITT
4.2.1.6	Proportion of Participants Achieving EASI75 by Prior Systemic Therapy	ITT
4.2.1.7	Proportion of Participants Achieving EASI75 by Season Enrolled	ITT
4.2.2	Proportion of Participants Achieving EASI50	ITT
4.2.3	Proportion of Participants Achieving EASI90	ITT
4.2.4	Mean and Standard Error Plot of By-Visit EASI Score	ITT
4.2.5	Mean and Standard Error Plot of By-Visit Change From Baseline in EASI Score	ITT
4.2.6	Proportion of Participants Achieving Both EASI75 and IGA-TS	ITT
4.2.7	Kaplan-Meier plot of time to open-label escape arm	ITT
4.2.8	Forest Plot of Response Rate Difference in Achieving EASI75 at Week 8	ITT
ITCH NRS Score		
4.3.1	Proportion of Participants Achieving $\geq 4$ -Point Improvement in Itch NRS Score in the VC Period	ITT
4.3.2	Proportion of Participants with ITCH4 From Day 1 to Day 7 in the VC Period	ITT
4.3.3	Mean and Standard Error Plot of By-Visit Itch NRS Score in the VC period	ITT
4.3.4	Mean and Standard Error Plot of By-Visit Change From Baseline in Itch NRS Score in the VC period	ITT
4.3.5	Mean and Standard Error Plot of By-Visit Itch NRS Score in the VCE period	VCE Primary
4.3.5	Kaplan-Meier Plot of Time to $\geq 2$ -Point Improvement in Itch NRS Score in the VC Period	ITT
4.3.6	Kaplan-Meier Plot of Time to $\geq 4$ -Point Improvement in Itch NRS Score in the VC Period	ITT
4.3.7	Mean and Standard Error Plot of By-Visit Daily Itch NRS Score in the VC Period	ITT
4.3.8	Mean and Standard Error Plot of By-Visit Change from Baseline in Daily Itch NRS Score in the VC Period	ITT
SCORAD		
4.4.1	Mean and Standard Error Plot of By-Visit SCORAD Total Score	ITT
4.4.2	Mean and Standard Error Plot of By-Visit Change From Baseline in SCORAD Total Score	ITT
Current Itch NRS		
4.5.1	Mean and Standard Error Plot of By-Timepoint Current Itch on Day 1	ITT
4.5.2	Mean and Standard Error Plot of By-Timepoint Change From Baseline in Current Itch on Day 1	ITT

Figure No.	Title	Population
4.5.3	Proportion of Participants achieving $\geq 2$ -Point Improvement in Current Itch NRS Score	ITT
4.5.4	Proportion of Participants achieving $\geq 4$ -Point Improvement in Current Itch NRS Score	ITT
Skin Pain NRS Score		
4.6.1	Mean and Standard Error Plot of By-Visit Skin Pain NRS Score	ITT
4.6.2	Mean and Standard Error Plot of By-Visit Change From Baseline in Skin Pain NRS Score	ITT
4.6.3	Mean and Standard Error Plot of By-Visit Daily Skin Pain NRS Score in the VC Period	ITT
4.6.4	Mean and Standard Error Plot of By-Visit Change From Baseline in Daily Skin Pain NRS Score in the VC Period	ITT
DLQI		
4.7.1	Mean and Standard Error Plot of By-Visit Total DLQI Score	ITT
4.7.2	Mean and Standard Error Plot of By-Visit Change From Baseline in Total DLQI Score	ITT
4.7.3	Proportion of Participants Achieving $\geq 4$ -Point Improvement in DLQI From Baseline	ITT
Patient-Oriented Eczema Measure		
4.8.1	Mean and Standard Error Plot of By-Visit POEM Score	ITT
4.8.2	Mean and Standard Error Plot of By-Visit Change From Baseline in POEM Score	ITT
EQ-5D-5L		
4.9.1	Mean and Standard Error Plot of By-Visit EQ-5D-5L VAS Score	ITT
4.9.2	Mean and Standard Error Plot of By-Visit Change From Baseline in EQ-5D-5L VAS Score	ITT
WPAI-AD		
4.10.1	Mean and Standard Error Plot of By-Visit WPAI-AD Score	ITT
4.10.2	Mean and Standard Error Plot of By-Visit Change From Baseline in WPAI-AD Score	ITT
PROMIS		
4.11.1	Mean and Standard Error Plot of By-Visit PROMIS Short Form- Sleep-Related Impairment 8a Score	ITT
4.11.2	Mean and Standard Error Plot of By-Visit Change From Baseline in PROMIS Short Form- Sleep-Related Impairment 8a Score	ITT
4.11.3	Mean and Standard Error Plot of By-Visit PROMIS Short Form Sleep Disturbance 8b Score	ITT
4.11.4	Mean and Standard Error Plot of By-Visit Change From Baseline in PROMIS Short Form Sleep Disturbance 8b Score	ITT
Hospital Anxiety and Depression Scale		
4.12.1	Mean and Standard Error Plot of By-Visit HADS Score	ITT
4.12.2	Mean and Standard Error Plot of By-Visit Change From Baseline in HADS Score	ITT
BSA		
4.13.1	Mean and Standard Error Plot of By-Visit Total %BSA Affected by AD	ITT
4.13.2	Mean and Standard Error Plot of By-Visit Change From Baseline in Total %BSA Affected by AD	ITT
4.13.3	Mean and Standard Error Plot of By-Visit Change From Baseline in the Number of Intertriginous Regions With Active AD Involvement	ITT
Laboratory		
4.14.1.X	Box Plot of Selected Hematology Results by Visit in the VC Period	Safety
4.14.2.X	Box Plot of change from baseline in Selected Hematology Results by Visit in the VC Period	Safety
4.14.3.X	Box Plot of Percentage Change from Baseline in Selected Hematology Results by Visit in the VC Period	Safety
Vital Signs		
4.15.1.X	Box Plot of Systolic Blood Pressure in the VC Period	Safety
4.15.2.X	Box Plot of Diastolic Blood Pressure in the VC Period	Safety
4.15.3.X	Box Plot of Pulse in the VC Period	Safety

Figure No.	Title	Population
4.15.4.X	Box Plot of Respiratory Rate in the VC Period	Safety
4.15.5.X	Box Plot of Body Temperature in the VC Period	Safety

## Listings

Listing No.	Title
Baseline Demographic and Characteristic	
2.1.1.1	Participant Enrollment and Disposition Status in the VC Period
2.1.1.2	Participant Enrollment and Disposition Status in the VCE Primary
2.1.1.3	Participant Enrollment and Disposition Status in the VCE Escape
2.1.2	Participant Inclusion and Exclusion Criteria Violations
2.2	Protocol Deviations
2.3	Analysis Populations
2.4.1	Demographic Characteristics
2.4.2	Baseline Disease Characteristics
2.4.3	Prior and Concomitant Medications
2.4.4	Prior Therapies for Atopic Dermatitis
2.4.5	Medical History
2.5.1	Study Drug Exposure and Compliance in the VC Period
2.5.2	Study Drug Exposure in the VCE Primary
2.5.3	Study Drug Exposure in the VCE Escape
2.5.4	Study Drug Exposure from Baseline to Week 24
Efficacy	
2.6.1	IGA Score
2.6.2	EASI
2.6.3.1	Itch NRS Daily Score
2.6.3.2	Itch NRS By-Visit Score
2.6.3.3	Time to Itch Response
2.6.4	SCORAD scores
2.6.5	Current Itch NRS
2.6.6.1	Skin Pain NRS Daily Score
2.6.6.2	Skin Pain NRS By-Visit Score
2.6.7	DLQI Score
2.6.8	POEM Score
2.6.9	EQ-5D-5L
2.6.10	WPAI-AD score
2.6.11	PROMIS Short Form– Sleep Disturbance 8b Score
2.6.12	PROMIS Short Form– Sleep-Related Impairment 8a Score
2.6.13	HADS Scores
2.6.14	Atopic Dermatitis Affected Percent BSA
2.6.15	Time to Open-Label Escape Arm
2.6.16	Time to First Re-Treatment in the VCE Period
2.6.17	Time to Concurrently Meeting All of the Following Criteria: IGA Score $\geq 3$ , EASI Score $\geq 16$ , Itch NRS Score $\geq 4$ , BSA $\geq 10\%$ , and DLQI Score $> 10$
2.6.18	Relapse After Study Treatment Discontinuation
2.6.19	Proportion of Study On and Off Study Treatment During VCE Period
2.6.20	Intertriginous Regions With Active AD Involvement
Adverse Events	
2.7.1	Adverse Events
2.7.2	Adverse Events Leading to Study Drug Discontinuation

Listing No.	Title
2.7.3	Serious Adverse Events
2.7.4	Treatment-Related Adverse Events
2.7.5	Adverse Events With a Fatal Outcome
2.7.6	Adverse Events Leading to Interruption of Study Drug
2.7.7	Grade 3 or Higher Adverse Events
2.7.8	Application Site Reactions
2.7.9	Adverse Events of Interest
Laboratory Data	
2.8.1	Clinical Laboratory Values – Hematology
2.8.2	Clinical Laboratory Values – Chemistry
2.8.3	Abnormal Clinical Laboratory Values – Hematology
2.8.4	Abnormal Clinical Laboratory Values – Chemistry
Vital Signs	
2.10.1	Vital Signs
2.10.2	Abnormal Vital Sign Values
2.10.3	Alert Vital Sign Values

## APPENDIX B. SAS CODE FOR MULTIPLE IMPUTATION

The following sample SAS code will be used for the MI of IGA:

```
proc mi data=mi_wide seed=184243261 nimpute=40 out=impute_IGA;  
  class trt01p strat1 strat2;  
  var trt01p strat1 Strat2 avalBASELINE avalWEEK2 avalWEEK4 avalWEEK8;  
  fcs REGPMM;  
  
run;
```

The following sample SAS code will be used for the MI of EASI:

```
proc mi data=mi_wide seed=184243262 nimpute=40 out=impute_EASI;  
  class trt01p strat1 strat2;  
  var trt01p strat1 Strat2 avalBASELINE avalWEEK2 avalWEEK4 avalWEEK8;  
  fcs;  
  
run;
```

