5. STUDY POPULATION

Deviations from eligibility criteria are not allowed because they can potentially jeopardize the scientific integrity of the study, regulatory acceptability, and/or participant safety. Therefore, adherence to the criteria as specified in this Protocol is essential. Prospective approval of Protocol deviations to recruitment and enrollment criteria, also known as Protocol waivers or exemptions, are not permitted.

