5.1. Inclusion Criteria

Participants are eligible to be included in the study only if all of the following criteria apply:

1. Adults aged ≥ 18 years at screening (Note: Legal adult age for Korea is ≥ 19 years).
2. Diagnosis of AD as defined by the Hanifin and Rajka (1980) criteria.
3. AD duration of at least 2 years.
4. IGA score of 3 at screening and Day 1.
5. EASI score > 7 at screening and Day 1.
6. Itch NRS score ≥ 4 at Day 1, defined as the average of the 7 days directly before Day 1, with Itch NRS values available for at least 4 of the 7 days.
7. %BSA (excluding the scalp) with AD involvement of at least 10% and up to 20% at screening and Day 1.
8. DLQI score > 10 at screening and Day 1.
9. Documented recent history (within 12 months before the screening visit) of inadequate response, intolerance, or contraindication to TCSs and TCIs (see Section 6.6.1) as follows:
 - a. Inadequate response:
 - For TCSs: Inability of a given TCS to induce and maintain remission or to contain the AD severity at an acceptable level (comparable to IGA score of 0 [clear] or 1 [almost clear]) despite treatment for 28 days or for the maximum duration recommended by the product prescribing information (eg, 14 days for superpotent TCSs), whichever is shorter
and
 - For TCIs: Inability of a given TCI to induce and maintain remission or to contain the AD severity at an acceptable level (comparable to IGA score of 0 [clear] or 1 [almost clear]) despite treatment according to the product prescribing information.

Note: Documented (within 12 months before the screening visit) systemic treatment for AD (eg, oral corticosteroids, cyclosporine, methotrexate, azathioprine, mycophenolate mofetil) or phototherapy or photo(chemo)therapy can also be considered as a surrogate for inadequate response to TCSs and TCIs.

- b. Intolerance: Clinically relevant side effects, safety risks, or skin tolerability issues that outweigh the potential treatment benefits and are the reason why a topical treatment could not be restarted or continued.

Note: Documented history (more than 12 months prior to the screening visit) of clinically significant adverse reactions with use of TCSs and/or TCIs that in the opinion of the investigator outweigh the benefits of restarting treatment would also be considered as evidence of intolerance.

- c. Contraindication: As defined in the product prescribing information.

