8.2.3. Investigator's Global Assessment

Investigator's Global Assessment is an overall eczema severity rating on a 0 to 4 scale that will be assessed during site visits (see [Table 3](#) and [Table 4](#)). The severity grades for the IGA are shown in [Table 8](#).

Table 8: Investigator's Global Assessment

Grade	Severity	Status
0	Clear	No erythema or induration/papulation, no oozing/crusting; there may be minor residual discoloration
1	Almost clear	There may be trace faint pink erythema, with almost no induration/papulation, and no oozing/crusting
2	Mild	There may be faint pink erythema, with mild induration/papulation and no oozing/crusting
3	Moderate	There may be pink-red erythema with moderate induration/papulation and there may be some oozing/crusting
4	Severe	There may be deep or bright red erythema with severe induration/papulation and with oozing/crusting

Source: [FDA 2022](#).

The IGA-TS is defined as an IGA score of 0 or 1 with a ≥ 2 -grade improvement from baseline.

Participants must have an IGA score of 3 at the screening and baseline visits to enroll in the study; they may have an IGA score of 0 to 4 at Week 8 to continue into the VCE period.

During the VCE period, including Week 8, IGA scores will be evaluated by the investigator to determine whether the participant requires continuation of treatment or should (re)enter an observation/no treatment period. If the IGA score is ≥ 1 , the participant will start or continue study cream BID. If the IGA score is 0 (clear), the participant will (re)enter an observation/no treatment period.

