#### **7.3.4.2. Multiple Imputation**

Multiple imputation will be used as an alternative method to handle missing data. A full conditional specification method ([van Buuren 2007](#)) that assumes the existence of a joint distribution for all variables will be used to impute the IGA or EASI score. A regression model including treatment group, stratification factors and baseline and scheduled postbaseline scores up to Week 8 will be specified for the fully conditional specification method. The imputation will be repeated a number of times to generate corresponding complete datasets in order to reflect the uncertainty around the true values. An example of the multiple imputation SAS code is provided in [Appendix B](#). The coprimary endpoints binary response will be derived for each of the imputed datasets per the definition in Sections 7.3.1.1 and 7.3.1.2. Regardless of MI imputed values, subjects with a missing Week 8 IGA and EASI assessments after discontinuation from treatment due to lack of efficacy or adverse event will be counted as nonresponders. The CMH test in Section 7.3.2 will be applied to each of the imputed datasets. The results will then be combined for the inference using Rubin's rule for each of the coprimary endpoints.

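### The IGA multiple-imputation model uses a baseline score that eligibility fixes at 3 and takes baseline EASI only as a two-level stratum; adding the continuous EASI scores is a small, free improvement

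*SAP*

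**What the plan says.** SAP 7.3.4.2 plans multiple imputation as an alternative to the primary nonresponder imputation (NRI) for both coprimary endpoints. IGA and EASI are imputed in separate runs. The text gives the model as: "A regression model including treatment group, stratification factors and baseline and scheduled postbaseline scores up to Week 8 will be specified".

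Appendix B supplies the code. The IGA run is introduced with "The following sample SAS code will be used for the MI of IGA", and its variable list is "var trt01p strat1 Strat2 avalBASELINE avalWEEK2 avalWEEK4 avalWEEK8". The EASI run has the same list. Both use 40 imputations; the IGA run uses predictive mean matching.

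The two strata are baseline EASI, cut at 16, and geographic region (SAP 3.1 and 7.3.4.1).

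The Protocol fixes baseline IGA. Section 5.1, criterion 4, requires "IGA score of 3 at screening and Day 1", and Section 8.2.3 repeats it: "Participants must have an IGA score of 3 at the screening and baseline visits to enroll in the study". Section 5 rules out waivers: "Deviations from eligibility criteria are not allowed because they can potentially jeopardize the scientific integrity of the study". Baseline EASI only has a floor, "EASI score > 7 at screening and Day 1", so it varies. Protocol Table 3 schedules IGA and EASI at the same visits.

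SAP 7.3.4.2 also sets a missing Week 8 result to nonresponse, whatever the model imputes, when it follows discontinuation for lack of efficacy or an adverse event.

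**The concern.** One variable list serves two scores for which the baseline term behaves differently. In the EASI run the baseline value differs between participants. In the IGA run it is 3 for everyone correctly enrolled, so it cannot help to predict Week 8 IGA. The IGA model's baseline severity information is then only the two-level EASI stratum, although a finer score on a 0 to 72 scale is recorded at every one of these visits.

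At stake is how well the analysis tests IGA-TS against missing data. Multiple imputation assumes data are missing at random given the variables in the model, and that is easier to defend when the model holds the predictors already collected. After the override for lack of efficacy and adverse events, the imputed values that count belong to people missing for other reasons. Someone lost before Week 2 is imputed from arm, region and EASI stratum alone.

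The analysis carries some weight. SAP 7.3.4 specifies no tipping-point analysis, and Appendix A lists a multiple-imputation table for IGA-TS (Table 2.1.2) but none for the longitudinal logistic model.

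**Working it through.** **1. The plan's own figure.** Inputs from Protocol Table 9: IGA-TS 60% vs 10%, 150 vs 75 participants (225 at 2:1), Fisher exact test, two-sided alpha 0.05. Power is the sum of Binomial(150, 0.60) × Binomial(75, 0.10) probabilities over all outcomes with Fisher p ≤ 0.05. The result is above 99.99%, which agrees with the stated > 95%. If 20% in each arm became nonresponders (0.60 × 0.80 = 0.48; 0.10 × 0.80 = 0.08), power would still exceed 99.99%.

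**2. What the constant adds.** Take the predictors of Week 8 IGA for 225 participants: intercept, treatment, two strata, baseline IGA = 3, Week 2 IGA, Week 4 IGA. That is 7 columns with rank 6. Without baseline IGA the rank is still 6.

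**3. What the EASI stratum keeps.** The documents give no EASI distribution. Assume a normal score with a proportion p at or above 16. The share of its variance kept by a binary split is φ(c)² / [p(1 − p)], with c the upper-p normal quantile.

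| p (assumed) | share kept |
|---|---|
| 0.10 | 0.34 |
| 0.20 | 0.49 |
| 0.30 | 0.58 |
| 0.40 | 0.62 |
| 0.50 | 0.64 |

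Baseline EASI is therefore coarsened, not absent.

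**4. Effect on the estimate, Weeks 2 and 4 observed.** The documents give no missing-data rate and no IGA–EASI correlation, so this is illustrative. A latent-severity model gave IGA-TS of about 61% vs 10%. Its Week 8 severity was 0.25 × baseline EASI (standardised) + 0.75 × a person effect + 0.6 × noise, less the treatment shift. The within-arm correlation with baseline EASI is then 0.25 / √(0.0625 + 0.5625 + 0.36) = 0.25. Week 8 values were removed at a base rate of 5%, 10% or 20%, either completely at random (MCAR) or depending on Week 4 IGA or Week 4 EASI. Imputation was by predictive mean matching, with 20 imputations and 200 trials per row.

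| Missingness, base rate | Difference, planned | Difference, + EASI | Shift | RMSE, planned | RMSE, + EASI | Fall |
|---|---|---|---|---|---|---|
| MCAR 5% | 0.5024 | 0.5024 | 0.0000 | 0.0115 | 0.0114 | 0.9% |
| MCAR 10% | 0.5058 | 0.5061 | +0.0003 | 0.0152 | 0.0150 | 1.3% |
| MCAR 20% | 0.5017 | 0.5008 | −0.0009 | 0.0251 | 0.0240 | 4.4% |
| Week 4 IGA 5% | 0.4966 | 0.4960 | −0.0006 | 0.0118 | 0.0115 | 2.5% |
| Week 4 IGA 10% | 0.5081 | 0.5076 | −0.0005 | 0.0186 | 0.0176 | 5.4% |
| Week 4 IGA 20% | 0.5081 | 0.5060 | −0.0021 | 0.0265 | 0.0245 | 7.5% |
| Week 4 EASI 5% | 0.5045 | 0.5038 | −0.0007 | 0.0103 | 0.0101 | 1.9% |
| Week 4 EASI 10% | 0.5028 | 0.5021 | −0.0007 | 0.0164 | 0.0159 | 3.0% |
| Week 4 EASI 20% | 0.5108 | 0.5100 | −0.0008 | 0.0238 | 0.0224 | 5.9% |

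RMSE is against the complete-data difference in the same trial. The largest fall in the standard error was 0.0572 − 0.0564 = 0.0008. Deleting the constant alone moved the mean difference by at most 0.0004 (for example 0.5024 to 0.5020).

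**5. Participants with no postbaseline score.** A separate simulation (1,500 trials, 10 imputations, IGA-TS about 56% vs 15%, 9% missing, missingness depending on EASI) covered this case. Imputed IGA-TS was too high by 3.6 points from arm and strata alone, and by 0.6 points with continuous baseline EASI added. RMSE of the rate difference fell from 2.2 to 1.8 points (0.4 / 2.2 = 18%). With Weeks 2 and 4 observed, the same simulation gave 1.28 to 1.21 points (0.07 / 1.28 = 5.5%), in line with step 4.

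**The case against.** The strongest reply is that nothing here is mis-specified. The SAP text and code agree. The model contains every variable in the CMH analysis, namely treatment and both strata, plus the history of the score being imputed. Auxiliary variables are a refinement. This stands, and it is why the point is minor.

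The reply also limits the size. The 3.6 points apply only to an assumed group with no postbaseline score and to missingness built to depend on EASI. If they are an error among the imputed participants, 9% missing makes them 0.09 × 3.6 = 0.3 points in the overall rate. Neither simulation applied the nonresponder override, which would take out part of the severity-driven dropout, and both used fewer than the planned 40 imputations. Because IGA and EASI share visits, a missed visit usually loses both, so Week 2 and Week 4 EASI cannot help someone with no postbaseline data; only continuous baseline EASI can. All of this stands.

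Two stronger readings are tempting. A reader might infer that EASI is left out of the IGA model; it is not, because one stratification factor is baseline EASI. A reader might also infer that conditioning on a constant biases or breaks the analysis. The model also conditions on arm, strata and IGA at Weeks 2 and 4, removing the constant changed nothing of note, and nothing in the documents shows a software failure.

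The reply does not remove the improvement itself: the baseline term is empty, a finer score is already in the database, and using it lowered RMSE in every scenario tried.

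**Conclusion.** The point holds as a minor, free improvement to one sensitivity analysis. Baseline IGA adds nothing to the IGA imputation model, and baseline EASI is used only as a two-level stratum while the continuous scores go unused.

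With Weeks 2 and 4 observed, adding EASI moved the rate difference by about 0.002 or less, against a planned difference of 0.50. It cut RMSE by about 4% to 8% at a 20% base missing rate and by about 1% to 5% at lower rates. The gain is larger for participants with no postbaseline score, but the documents do not say how many to expect. These sizes rest on assumed missingness and an assumed link between IGA and EASI.

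A reader should not infer that the IGA-TS conclusion is at risk. The primary NRI analysis does not use this model, the EASI run is sound on this point, and no stated figure is wrong. A participant enrolled in error with another baseline IGA would make the term vary, but a coefficient resting on one or two such people would be of no use.

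**What to change.** Before unblinding:

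- In the Appendix B IGA code, remove baseline IGA from the variable list and add continuous EASI at baseline, Week 2 and Week 4. Alternatively, impute IGA and EASI together in one fully conditional run, keeping predictive mean matching for IGA.
- Keep treatment, both strata and the nonresponder override for lack of efficacy and adverse events.
- Keep baseline IGA in the dataset, since IGA-TS is derived from it after imputation.
- Reword the model sentence in SAP 7.3.4.2 to name the EASI scores for the IGA run.

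The cost is one line of code and one SAP sentence, with no new data. If unblinding has already happened, run the planned model as written and report the extended one beside it, labelled post hoc.

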10. STATISTICS

10.1. Sample Size Determination

Approximately 225 participants will be enrolled in this study and randomized 2:1 to ruxolitinib 1.5% cream or vehicle cream and stratified by baseline EASI score (< 16 or ≥ 16) and geographic region (ROW or Europe).

The sample size was calculated to provide sufficient power to detect a difference between the treatment groups in the coprimary and key secondary endpoints. The assumptions and powers for different endpoints are provided in [Table 9](#). The assumed response rates are derived from the overall and subgroup analyses (population: baseline scores of Itch NRS ≥ 4 , EASI > 7 , post-TCS and -TCI, and IGA = 3) in 2 Phase 3 AD studies, INCB 18424-303 and INCB 18424-304. Fisher exact test was used to provide a conservative evaluation of statistical power. Using a 2-sided α of 0.05, the sample size will have $> 95\%$ power to detect a difference in the coprimary endpoints, EASI75 and IGA-TS response rates between the treatment groups, and $> 95\%$ power for all key secondary endpoints.

In addition to providing sufficient power for efficacy variables, the sample size will provide an adequate database for safety evaluations.

Table 9: Powering for Coprimary and Key Secondary Endpoints

Variable	Response Rates in Ruxolitinib 1.5% BID	Response Rates in Vehicle	Power: Ruxolitinib vs Vehicle
EASI75	70%	15%	$> 95\%$
IGA-TS	60%	10%	$> 95\%$
ITCH4 at Week 8	50%	15%	$> 95\%$
ITCH4 on Day 7	40%	12%	$> 95\%$
ITCH4 on Day 3	35%	10%	$> 95\%$
ITCH4 on Day 2	20%	3%	$> 95\%$

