### 3.3. Sample Size Considerations

Approximately 225 participants will be enrolled in this study and randomized 2:1 to ruxolitinib 1.5% cream or vehicle cream and stratified by baseline EASI score ( $< 16$  or  $\geq 16$ ) and geographic region (ROW or Europe).

The sample size was calculated to provide sufficient power to detect a difference between the treatment groups in the coprimary and key secondary endpoints. The assumptions and powers for different endpoints are provided in [Table 2](#). The assumed response rates are derived from the overall and subgroup analyses (population: baseline scores of Itch NRS  $\geq 4$ , EASI  $> 7$ , post-TCS and -TCI, and IGA = 3) in 2 Phase 3 AD studies, INCB 18424-303 and INCB 18424-304. Fisher

exact test was used to provide a conservative evaluation of statistical power. Using a 2-sided  $\alpha$  of 0.05, the sample size will have > 95% power to detect a difference in the coprimary endpoints, EASI75 and IGA-TS response rates between the treatment groups, and > 95% power for all key secondary endpoints.

In addition to providing sufficient power for efficacy variables, the sample size will provide an adequate database for safety evaluations.

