**Table 2: Powering for Coprimary and Key Secondary Endpoints**

Variable	Response Rates in Ruxolitinib 1.5% BID	Response Rates in Vehicle	Power: Ruxolitinib vs Vehicle
EASI75	70%	15%	> 95%
IGA-TS	60%	10%	> 95%
ITCH4 at Week 8	50%	15%	> 95%
ITCH4 on Day 7	40%	12%	> 95%
ITCH4 on Day 3	35%	10%	> 95%
ITCH4 on Day 2	20%	3%	> 95%

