### **7.3.4. Sensitivity and Supportive Analyses for the Coprimary Endpoints**

#### **7.3.4.1. Longitudinal Logistic Regression With Repeated Measures**

To adjust for the dependence underlying the hierarchical multilevel data structure (visit, participant, and site), a longitudinal logistic regression with repeated measures will be applied in both of the coprimary endpoints. The 3 level structures in the model are as follows:

- Level 1: visit
- Level 2: participant
- Level 3: site

where visits are nested within participants, which are further nested within sites.

The binary response (IGA-TS or EASI75) of each participant at Week 2, Week 4, and Week 8 will be included as the dependent variable. Treatment (1.5% BID and vehicle BID), the randomization stratification factors (baseline EASI and geographic region), visit, and treatment-by-visit interaction will be included as fixed effects. Site level intercept and participant nested in site level intercept will be included as random effects. The within-participant and within-site errors will be modeled by an unstructured variance-covariance matrix. The Kenward-Roger approximation will be used to estimate denominator degrees of freedom for this model.

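### The EASI multiple imputation uses plain linear regression where IGA uses predictive mean matching, which understates EASI75 on ruxolitinib; the repeated-measures logistic model carries one redundant covariance term (minor)

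*SAP*

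**What the plan says.** SAP 7.3.4 gives two sensitivity methods for the coprimary endpoints.

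- **Multiple imputation (7.3.4.2, Appendix B).** IGA and EASI scores are imputed by fully conditional specification. The regression uses treatment, the stratification factors, baseline, and scheduled scores to Week 8. EASI75 and IGA-TS are then derived, and the CMH results are combined by Rubin's rule. The IGA code specifies `REGPMM`. The EASI code, "proc mi data=mi_wide seed=184243262 nimpute=40 out=impute_EASI", is followed by a bare `fcs` with no method, bounds, rounding or transformation. Participants missing Week 8 after stopping for lack of efficacy or an adverse event count as nonresponders whatever value is imputed.
- **Longitudinal logistic model (7.3.4.1).** The responses are the binary outcomes at Weeks 2, 4 and 8. On random effects: "Site level intercept and participant nested in site level intercept will be included as random effects". On the errors: "The within-participant and within-site errors will be modeled by an unstructured variance-covariance matrix". No fallback is given.

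SAP 7.3.1.1 gives EASI a range of 0 to 72 and defines EASI75 as an improvement of at least 75%. Entry requires EASI above 7 (Protocol 5.1).

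**The concern.** With 70% of the ruxolitinib arm expected to improve by at least 75%, Week 8 EASI in that arm should pile up close to 0 with a right tail. A linear model with one residual SD shared by both arms replaces that shape with a symmetric, wider one. Part of it falls below 0, and too much falls above the EASI75 cut-off. The imputed response rate on ruxolitinib is then too low for a reason unrelated to why data are missing. A sensitivity analysis should show what the missing data could do, not what a poorly fitting imputation model does. The SAP gives no reason for treating EASI differently from IGA.

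In the logistic model, an unstructured matrix over three visits already describes all the within-participant covariance. A participant intercept describes part of it again. If the fit has to be simplified, nothing says how, so the choice could be made after the results are seen.

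**Working it through.** **1. The plan's own figure.** "Approximately 225 participants will be enrolled in this study and randomized 2:1 to ruxolitinib 1.5% cream or vehicle cream", that is 150 and 75. Exact two-sided Fisher power at 0.05 (Protocol 10.1: "Fisher exact test was used to provide a conservative evaluation of statistical power"):

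- "EASI75 70% 15% > 95"%: recomputed >99.9%
- IGA-TS: >99.9%
- ITCH4 at Week 8, Day 7 and Day 3: 99.98%, 99.6% and 99.1%
- "ITCH4 on Day 2 20% 3% > 95"%: recomputed 97.8%

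All six exceed 95%, so the stated power reproduces. Nothing below changes it.

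**2. Why the linear model misses, by hand.** These inputs are assumed, because the documents give no EASI mean or SD. Take a baseline of 11, so the EASI75 cut-off is 0.25 × 11 = 2.75. Calibrating skewed scores to 70% and 15% EASI75 (SD of log Week 8/baseline ratio 0.7) gave a Week 8 mean (SD) of 2.4 (2.0) on ruxolitinib and an SD of 4.9 on vehicle.

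- Pooled SD = √[(150 × 2.0² + 75 × 4.9²)/225] = √10.67 = 3.27.
- P(score ≤ 2.75) = Φ[(2.75 − 2.4)/3.27] = Φ(0.11) ≈ 54%, not 70%.
- P(score < 0) = Φ(−2.4/3.27) = Φ(−0.73) ≈ 23%.

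This ignores the spread of baseline scores and the information from Weeks 2 and 4, but it shows the mechanism.

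**3. Simulation.** Assumptions:

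- baseline mean (SD) 11 (3) or 14 (5)
- log-SD 0.7 or 1.0
- Week 2 and Week 4 EASI75 of 40%/6% and 58%/10%
- 5, 10 or 20% missing at random at Week 8
- no nonresponder override

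Each scenario had 25-30 trials with 10 imputations each. Results at 10% missing, in %:

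| log-SD, baseline | negative, imputed ruxolitinib (linear) | EASI75, imputed ruxolitinib: linear / PMM / true | ITT difference: linear / PMM / full data |
|---|---|---|---|
| 0.7, 11 (3) | 21.6 | 57.5 / 73.7 / 70.9 | 54.3 / 55.5 / 55.4 |
| 0.7, 14 (5) | 21.9 | 55.1 / 68.2 / 70.6 | 54.3 / 55.2 / 55.3 |
| 1.0, 11 (3) | 25.1 | 50.8 / 67.5 / 68.0 | 52.3 / 53.4 / 53.8 |
| 1.0, 14 (5) | 27.5 | 51.7 / 68.2 / 71.2 | 53.9 / 54.9 / 55.5 |

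Over all 12 scenarios, linear imputation gave 51-58% EASI75 among imputed ruxolitinib participants, against 66-74% with predictive mean matching (PMM) and 68-73% true. The ITT difference fell short of the full-data value by 0.3 to 2.7 points with linear imputation and by at most 0.7 with PMM. Further runs with log-SD 0.5-1.1 and 10% missing gave 51-65% against about 70% true. The shortfall among the imputed is therefore about 5 to 20 points.

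Precision is modest. With 25 trials and 15 missing per trial, the SE of a true rate is √(0.7 × 0.3/375) ≈ 2.4 points.

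**4. Link to the ITT difference.** Arm effect = missing fraction × shortfall. Second row: ruxolitinib 0.10 × (70.6 − 55.1) = 1.55 points; vehicle 0.10 × (16.4 − 11.3) = 0.51. Net 1.04, matching 55.3 − 54.3 = 1.0. If half of the missing cases fall under the override (an assumption), the ruxolitinib term halves to about 0.78.

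**5. Role of negative values.** Over wider settings (log-SD 0.4-1.3, baseline mean up to 18, visit correlation up to 0.9, 10% missing), 6-28% of imputed ruxolitinib scores were negative, or 0.8 to 4.3 values per completed dataset. Setting them to 0 changed no EASI75 classification.

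**6. Logistic model.** An unstructured matrix for 3 visits has 3 × 4/2 = 6 parameters. Adding 1 participant and 1 site variance gives 8. The Jacobian of the implied covariance has rank 7: a participant variance added to every cell of the matrix gives another unstructured matrix. In a logistic model the two can be told apart only through the nonlinearity of the logit. There are 225 × 3 = 675 planned binary observations and about 225/100 = 2.25 participants per site.

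**The case against.** The strongest reply is that this hardly matters. The shift is at most about 3 points against an assumed difference of 70 − 15 = 55. It runs against the active arm, affects one supportive analysis of one coprimary endpoint, and shrinks under the override. All of that stands, and it sets the severity.

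Four stronger readings are tempting, and the documents do not support them.

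- *Negative scores corrupt EASI75.* They do not. By the SAP 7.3.1.1 definition a negative score is a responder exactly as 0 is. They are a symptom; the cause is the wrong shape and the shared variance.
- *The imputation of both coprimary endpoints is faulty.* The IGA imputation uses predictive mean matching and stays on its scale.
- *The logistic model will fail to converge.* Nobody has fitted it; only the parameters were counted. If the unstructured matrix was meant for the two scalar random intercepts alone, there are 2 parameters and no redundancy. The SAP's reference to errors does not support that reading, but the sponsor could clarify it.
- *No other missing-data check exists.* The per-protocol analysis excludes participants with missing coprimary data, and Protocol 10.4.1 allows a tipping-point analysis. However, the first also excludes for other deviations, and the second is optional and not taken up in SAP 7.3.4.

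That the logistic model yields a conditional odds ratio is a matter of preference. The primary analysis reports an odds ratio too.

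**Conclusion.** The point holds and is minor. As coded, the EASI imputation would understate EASI75 among imputed ruxolitinib participants by roughly 5 to 20 points. It would lower the ITT difference by about 0.3 to 3 points before the override, and by less after it. These sizes rest on assumed EASI distributions and 5-20% missing at random. The direction rests only on the 0 bound, the expected skew and the shared residual variance.

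The covariance specification in SAP 7.3.4.1 is redundant on its plain wording. Neither point alters the CMH test with nonresponder imputation or the power, so neither is a reason to doubt the primary result.

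**What to change.** In Appendix B, change the EASI statement to `fcs regpmm`, as for IGA, and state the number of donors for both, since the IGA code gives none. The cost is one keyword. Imputed scores are then limited to values actually observed.

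In SAP 7.3.4.1, keep one description of the within-participant dependence. For example, retain the site and participant random intercepts and drop the unstructured error matrix. Add a sentence giving the order of simplification if the model does not converge. The cost is a short paragraph, and the price is a more restrictive correlation pattern over the three visits.

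Replacing the model with generalised estimating equations is possible but is a trade-off, because the unweighted form needs a stronger missing-data assumption. Both changes should be made before the primary database lock.
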